5.3 Lifestyle restrictions

No restrictions required.

5.3.1 Meals and dietary restrictions

No restrictions required.

5.3.2 Caffeine, alcohol, and tobacco

No restrictions required.

5.3.3 Activity

No restrictions required.

5.4 Screen failures

Screen failures are defined as participants who consent to participate in the clinical study but are not subsequently randomly assigned to study medication. A minimal set of screen failure information is required to ensure transparent reporting of screen failure participants to meet the Consolidated Standards of Reporting Trials publishing requirements and to respond to queries from regulatory authorities. Minimal information includes demography, screen failure details, eligibility criteria, and any serious adverse event (SAE).

Individuals who do not meet the criteria for participation in this study (screen failure) may be rescreened once, in this case the study participant will be assigned a new number; information on the previous number must be recorded.

Study participants who require prophylaxis for LTBI must be on treatment for at least 4 weeks prior to initiation of IMP. These study participants may be rescreened once they have completed the first 4 weeks of prophylaxis treatment after consultation with the Medical Monitor.

Study participants who initiated treatment for latent TB infection (LTBI) during the Screening Period will be screening failures as TB treatment needs to be stable at least 4 weeks prior to first DZP dose. In the scope of rescreening the study participant must repeat initial screening laboratory parameters (except the interferon- γ release assay [IGRA] TB test), all physical examinations, and questionnaires (after completing at least 4 weeks of treatment for LTBI) at the rescreening visit prior to randomization in the study and must continue the full course of TB prophylactic therapy.

The Investigator must assess that the study participant's likelihood of completing the full course of TB prophylactic therapy is high and duly record their opinion in the study participant's record prior to randomizing the study participant.

6 STUDY TREATMENTS

Study treatment is defined as any investigational treatment(s), marketed product(s), placebo, or medical device(s) intended to be administered to a study participant according to the study protocol.

6.1 Treatments administered

Study participants will receive IMP by iv administration as a 2-hour infusion at the first administration Visit (V2, Baseline Visit), and then as a 1-hour infusion Q4W thereafter. Study participants will be observed for at least 1 hour after dosing for safety surveillance.

Serious [REDACTED] reactions (including [REDACTED]) and other infusion-related reactions have been reported following the initial and subsequent DZP and blinded study medication administrations [see IB Section 6.2.2]. Consider premedication by administration of an antihistamine, with or without paracetamol, before infusion of study medication, specifically before the first infusion and for study participants with a history of these reactions (see also Section 8.3.7 and Table 1-2, footnote x). However, available evidence is insufficient to determine to what extent premedication diminishes the frequency or severity of [REDACTED] reactions. Study medication must be administered by healthcare providers prepared to manage [REDACTED] reactions, including [REDACTED], and infusion-related reactions (see Table 1-2, footnote x). If a serious infusion-related or [REDACTED] reaction (eg, [REDACTED]) occurs,

immediately interrupt the administration of study medication and initiate appropriate therapy. In case of a suspected infusion reaction, blood samples should be obtained for a serum tryptase test (see Section 10.15.1).

Body weight will be measured at Screening to determine dosing through Week 20 and will be measured again at Week 24 to determine dosing for the rest of the study. (Exceptions: For participants screened under the initial protocol [ie, before Amendment 1], dosing through Week 20 will be determined using the Baseline body weight.)

Characteristics of the IMP are provided in [Table 6-1](#).

Table 6-1: Characteristics of IMP

ARM Name	DZP	PBO
Intervention name	DZP	PBO
Type	Biologic	PBO
Dose formulation	Lyophilized drug product in vial	Liquid
Dosage level(s)	24 mg/kg	NA
Route of administration	iv infusion	iv infusion
Infusion duration	Initial dose: 2 hours Follow up doses: 1 hour	Initial dose: 2 hours Follow up doses: 1 hour
Use	Experimental	Placebo comparator
Sourcing	Provided centrally by Sponsor	Provided centrally by Sponsor
Packaging and labeling	Packaging will be described in the IP Handling Manual Labeling will be as per country requirements	Packaging will be described in the IP Handling Manual Labeling will be as per country requirements
Current/Former name(s) or alias(es)	CDP7657	NA

DZP=dapirolizumab pegol; IMP=investigational medicinal product; IP=investigational product; iv=intravenous;
NA=not applicable; PBO=placebo

6.2 Preparation, handling, storage, and accountability requirements

In order to maintain blinding, an unblinded pharmacist or other suitably qualified site personnel will prepare each dose of IMP and provide the blinded and sealed infusion bag to the qualified site personnel performing the administration. The used blinded and sealed infusion bag is to be returned to the pharmacy or other unblinded designee to confirm the seal is not broken and blind is ensured outside the pharmacy. Complete preparation instructions will be outlined in the IP Handling Manual.

The Investigator or designee must confirm appropriate temperature conditions have been maintained during transit for all study medication received and any discrepancies are reported and resolved before use of the study medication.

Only participants randomized in the study may receive study medication and only authorized site staff may supply or administer study medication. All study medication must be stored in a secure, environmentally controlled, and monitored (manual or automated) area in accordance with the labeled storage conditions with access limited to the Investigator and authorized site staff.

The Investigator, institution, or the head of the medical institution (where applicable) is responsible for study treatment accountability, reconciliation, and record maintenance (ie, receipt, reconciliation, and final disposition records).

In case an out-of-range temperature is noted, it must be immediately reported as per instructions contained in the IP Handling Manual.

Further guidance and information for the final disposition of unused study treatment are provided in the IP Handling Manual.

6.2.1 Drug accountability

The electronic Case Report Form (eCRF) will be used to record study medication dispensing and return information on a by-participant basis. Details of any study medication lost, damaged (due to breakage or wastage), not used, partially used, disposed of at the study site, or returned to the Sponsor or designee must also be recorded on the appropriate forms. All supplies and pharmacy documentation must be made available throughout the study for UCB (or designee) to review.

The Investigator (or designee) is responsible for retaining all used, unused, and partially used containers of study medication until returned or destroyed.

The Investigator may assign some of the Investigator's duties for drug accountability at the study site to an appropriate pharmacist/designee.

The Investigator must ensure that the study medication is used only in accordance with the protocol.

Periodically, and/or after completion of the clinical phase of the study, all used (including empty containers)/partially used, unused, damaged, and/or expired study medication must be reconciled and either destroyed at the site according to local laws, regulations, and UCB standard operating procedures or returned to UCB (or designee). Investigational medicinal product intended for the study cannot be used for any other purpose than that described in this protocol.

6.3 Measures to minimize bias: randomization and blinding

All participants will be centrally assigned to randomized study medication using an Interactive Web Response System (IWRS). Before the study is initiated, the log in information and directions for the IWRS will be provided to each site.

The IWRS will assign eligible participants to a treatment regimen based on a predetermined production randomization and/or packaging schedule provided by UCB (or designee). The randomization schedule will be produced by the IWRS vendor. The IWRS will generate individual assignments for participant kits of IMP, as appropriate, according to the visit schedule. Participants' treatment assignment will be stratified by Pooled Region (North America vs Western Europe/Asia-Pacific vs Latin America/Eastern Europe), Screening disease activity (chronic active vs acute flaring) and Screening SLEDAI score (<10 vs ≥10), to ensure balanced

treatment allocation across the 12 subgroups. Each site enrollment of study participants will be limited to 5% of the total study population.

At Screening, each candidate participant will be assigned a 5-digit number that serves as the participant identifier throughout the study. The participant number will be required in all communication between the Investigator or designee and the IWRS regarding a particular participant.

Eligible participants will be randomized to treatment groups at the Baseline Visit (Day 1). The IWRS will allocate kit numbers to the participant based on the participant number during the course of the study. Participant numbers and kit numbers will be tracked via the IWRS.

Study medication will be dispensed at the study visits summarized in Schedule of Activities (Section 1.3).

To minimize bias, the same Investigator should perform the key efficacy assessments BILAG 2004 and SLEDAI-2K whenever possible and this will be documented in the database.

6.3.1 Procedures for maintaining and breaking the treatment blind

6.3.1.1 Maintenance of study treatment blind

All study participant treatment details will be allocated and maintained by the IWRS.

The following individuals will receive the randomization code at the start of the study:

- Sponsor and designated contract research organization (CRO) bioanalytical staff analyzing pharmacokinetic (PK) and ADA samples.
- Sponsor clinical trial supply staff
- IWRS provider

Study site pharmacists or other suitably qualified site personnel who are responsible for preparation of IMP treatments and any necessary assistants will have access to treatment allocations for individual study participants via the IWRS. The unblinded pharmacy monitors from the CRO, the Clinical Supply Manager, and the unblinded Clinical Project Manager (CPM) (or designee) will also have access to the treatment allocations and to the drug accountability records, if applicable.

The following individuals may have access to the randomization code as indicated:

- Sponsor Drug Safety staff as needed for reporting SAEs to regulatory authorities.
- On request, members of the IDMC (Section 9.7) who participate in unblinded (closed) sessions will be given information about the IMP allocation for those study participants for whom data are provided at these sessions.
- Sponsor and/or CRO staff supporting preparation of the initial biomarker analysis.
- Sponsor and/or CRO staff supporting preparation of the data outputs for the IDMC review.
- A Quantitative Clinical Pharmacologist/Modeling & Simulation Scientist may have access to the randomization code if PK data are requested for review by the IDMC.

Beside the exception of emergency unblinding of individual participants as described in Section 6.3.1.2, the following individuals will be unblinded to the treatment assignment. All other study personnel will remain blinded to the treatment assignment until the end of the study.

Key unblinded study personnel include:

- Study site pharmacists or other qualified site personnel who are responsible for the preparation and handling of IMP treatments
- Unblinded pharmacy monitors from the CRO
- Clinical Supply Manager
- Unblinded CPM
- Members of the IDMC who participate in unblinded sessions, and statistical team members who provide unblinded outputs (and are not involved in the study in any other way)
- A Quantitative Clinical Pharmacologist/Modeling & Simulation Scientist (separate from study team)
- Laboratory staff analyzing blood samples for [REDACTED] and ADA
- Sponsor pharmacovigilance staff reporting SUSARs to regulatory authorities

Should other study with DZP be performed at the same site, all efforts will be made to maintain the blinding at the site level as defined in this protocol as long as the study will be performed.

Under normal circumstances, the blinded treatment must not be revealed. It will be possible to break the blind, if medically indicated (Section 6.3.1.2). The impact on study conduct of this should be discussed in advance with the Medical Monitor or the Sponsor's Study Physician whenever possible.

6.3.1.2 Breaking the treatment blind in an emergency situation

If a situation arises in which it is medically indicated to determine the treatment (ie, knowledge of the nature and/or dose of the applied study medication determines decisions on further diagnostic procedures or treatment), it will be possible to determine to which treatment arm the study participant has been allocated during the Double-Blind Treatment Period by contacting the IWRS. All sites will be provided with details of how to contact the system for code breaking at the start of the study. Unblinding can be initiated by the Investigator at any time as medically indicated; however, whenever possible, the Medical Monitor or the Sponsor's Study Physician should be consulted prior to unblinding to discuss the impact on the study conduct.

The study team will be informed immediately via the IWRS when a code is broken, but will remain blinded to specific treatment information. Any unblinding of the IMP performed by the Investigator must be recorded in the source documents and on the Study Termination eCRF page.

6.4 Treatment compliance

The IMP will be administered by designated study site staff. The unblinded monitor will review the pharmacy records at each site, including the Drug Dispensing Record Form. The unblinded

monitor will compare the dispensing record and vials to the individual study participant's identifiers and visit schedule to assure that the study participant received the correct treatment and dose, and that the dosing schedule is correct. The unblinded monitor's report will include details of any missed doses, errors in dose, treatment errors or schedule errors, and reasons for these. All supplies and pharmacy documentation must be made available throughout the study for the unblinded monitor to review.

Study participants are expected to receive all doses of IMP as detailed in the schedule of assessments. Any study participants who deviate from the dosing schedule or miss any scheduled treatment should be reported to the Medical Monitor as soon as possible for determination of possible schedule adjustments and continued eligibility; these study participants should return to their original visit schedule. These instances will be handled on a case-by-case basis.

6.5 Concomitant medication(s)/treatment(s)

6.5.1 Permitted concomitant treatments (medications and therapies)

6.5.1.1 Corticosteroids

Corticosteroids are permitted during the study at any dose in the sense of escape medication, if medically indicated (see Section 6.6.2). At the screening visit (V1) corticosteroid dose must not exceed 40mg/day prednisone equivalent and must be stable for 2 weeks prior to Screening (approximately 4 weeks prior to Baseline Visit). Further, the dose must remain stable during Screening Period and should be kept stable onwards, if possible, or tapered. In case of a high corticosteroid dose (>20mg/day) an early start of tapering should be considered depending on the individual patient's condition. If the corticosteroid dose exceeds 7.5mg/day prednisone equivalent, it should be tapered in line with international treatment guidance as soon as possible, but must be initiated at the latest at Week 8 (V4). The timepoint and speed of tapering should be adapted to the individual study participant's condition (see below). Steroid doses should be converted to prednisone equivalent doses prior to the assessment of study participant inclusion criteria and initiation of corticosteroid tapering (regardless of route, except for intraocular, nasal, and topical). The list of corticosteroids and their corresponding prednisone equivalent doses can be found in [Table 6-2](#).

Table 6-2: Prednisone equivalent doses of systemic corticosteroids

Corticosteroids	Prednisone equivalent dose to 1mg of the listed corticosteroid dose
Cortisone	0.2mg
Hydrocortisone	0.25mg
Deflazacort	0.75mg
Prednisolone	1mg
Prednisone	1mg
Methylprednisolone	1.25mg
Triamcinolone	1.25mg
Dexamethasone	6.7mg

Table 6-2: Prednisone equivalent doses of systemic corticosteroids

Betamethasone	8.3mg
---------------	-------

To determine the prednisone equivalent dose of the corticosteroids shown on the left, multiply the mg dose of corticosteroid on the left by the dose amount in the corresponding right hand column. For example, a 0.8mg dose of methylprednisolone is equivalent to 1mg ($0.8\text{mg} \times 1.25$) of prednisone.

The dose of a specified corticosteroid that is equivalent to 1mg prednisone is given in [Table 6-3](#).

Table 6-3: Corticosteroid dose equivalent to 1mg prednisone

Corticosteroids	Corticosteroid dose equivalent to 1mg prednisone
Cortisone	5mg
Hydrocortisone	4mg
Deflazacort	1.3mg
Prednisolone	1mg
Prednisone	1mg
Methylprednisolone	0.8mg
Triamcinolone	0.8mg
Dexamethasone	0.15mg
Betamethasone	0.12mg

A pulse dose ($>500\text{mg} \times 1$ to 3 days) of iv corticosteroids should not have been given within the 4 weeks before screening.

Study participants not receiving concomitant corticosteroids or who were previously receiving corticosteroids on an as-needed basis must have stopped the treatment or been assigned to a continuous corticosteroid dose at least 2 weeks prior to Screening (Visit 1).

In study participants receiving concomitant corticosteroid doses $>7.5\text{mg/day}$ prednisone or equivalent, a mandatory corticosteroid taper must be initiated as early as possible but no later than 8 weeks after the first study medication infusion (Day 56). The tapering regimen will aim to reduce the daily prednisone equivalent dose to 7.5mg/day or lower by Week 18.

If such a rapid tapering is not considered by the Investigator to be appropriate for the individual study participant, a slower tapering regimen can be used.

Study participants achieving a dose of 7.5mg/day or lower may remain on this dose or continue to taper at the discretion of the Investigator. It is recommended to reduce the dose further in a slow manner.

Study participants whose disease is worsening after initiation of tapering and therefore cannot fulfill the taper based on the Investigator's judgment or whose corticosteroid dose has to be increased, if indicated, should remain in the study and receive corticosteroids at an appropriate

dose as determined by the Investigator. Study participants will be considered nonresponders for the primary endpoint in case of the intercurrent event escape treatment intervention with corticosteroids as outlined in Section 8.1.3.1.

Study participants will be issued a daily diary in which to record corticosteroid doses taken on a daily basis at home in between visits. Investigators are advised to contact the Medical Monitor or Sponsor's Study Physician upfront, if possible, to discuss the potential impact on the further study conduct in case use of oral or parenteral steroids for non-SLE related conditions is needed.

In case the corticosteroid dose at screening visit (V1) is not shown in the recommended tapering regimen table (Table 6-4), the tapering regimen of the next higher dose in the table should be used. Reduction of corticosteroids between Weeks 44 and 48 should be avoided.

This document cannot be used to support any marketing authorization application and any extensions or variations thereof.

PUBLIC COPY

Table 6-4: Recommended corticosteroid tapering schedule

Week	Day	Corticosteroid dose ^a (mg/day; prednisone equivalent)										
Starting Dose		40 ^a	35 ^a	30 ^a	25 ^a	20 ^a	15 ^a	10 ^a	7.5 ^b	5 ^b	2.5 ^b	0
1	Day 1 to Day 7	30	30	30	25	20	15	10	7.5	5	2.5	0
2	Day 8 to Day 14	30	20	30	25	20	15	10	7.5	5	2.5	0
3	Day 15 to Day 21	20	20	20	20	20	15	10	7.5	5	2.5	0
4	Day 22 to Day 28	20	15	20	20	20	15	10	7.5	5	2.5	0
5	Day 29 to Day 35	15	15	15	15	15	10	10/7.5 ^{b,c}	7.5 ^b	5 ^b	NA ^b	NA ^b
6	Day 36 to Day 42	15	10	15	15	15	10	10/7.5 ^{b,c}	7.5 ^b	5 ^b	NA ^b	NA ^b
7	Day 43 to Day 49	10	10	10	10	10	10 ^b	10/7.5 ^{b,c}	7.5/5 ^{b,c}	5 ^b	NA ^b	NA ^b
8	Day 50 to Day 56	10	10	10	10	10	10 ^b	10/7.5 ^{b,c}	7.5/5 ^{b,c}	5 ^b	NA ^b	NA ^b
9	Day 57 to Day 63	10	10/7.5 ^{b,c}	10	10	10	10/7.5 ^{b,c}	7.5 ^b	7.5/5 ^{b,c}	5 ^b	NA ^b	NA ^b
10	Day 64 to Day 70	10/7.5 ^{b,c}	10/7.5 ^{b,c}	10/7.5 ^{b,c}	10/7.5 ^{b,c}	10/7.5 ^{b,c}	10/7.5 ^{b,c}	7.5 ^b	7.5/5 ^{b,c}	5 ^b	NA ^b	NA ^b
11	Day 71 to Day 77	10/7.5 ^{b,c}	10/7.5 ^{b,c}	10/7.5 ^{b,c}	10/7.5 ^{b,c}	10/7.5 ^{b,c}	10/7.5 ^{b,c}	7.5 ^b	7.5/5 ^{b,c}	5 ^b	NA ^b	NA ^b
12	Day 78 to Day 84	10/7.5 ^{b,c}	10/7.5 ^{b,c}	10/7.5 ^{b,c}	10/7.5 ^{b,c}	10/7.5 ^{b,c}	10/7.5 ^{b,c}	7.5 ^b	7.5/5 ^{b,c}	5 ^b	NA ^b	NA ^b

Table 6-4: Recommended corticosteroid tapering schedule

Week	Day	Corticosteroid dose ^a (mg/day; prednisone equivalent)									
13	Day 85 to Day 91	10/7.5 ^{b,c}	7.5 ^b	10/7.5 ^{b,c}	10/7.5 ^{b,c}	10/7.5 ^{b,c}	7.5 ^b	7.5/5 ^{b,c}	5 ^b	5 ^b	NA ^b
14	Day 92 to Day 98	7.5 ^b	7.5 ^b	7.5 ^b	7.5 ^b	7.5 ^b	7.5 ^b	7.5/5 ^{b,c}	5 ^b	5 ^b	NA ^b
15	Day 99 to Day 105	7.5 ^b	7.5 ^b	7.5 ^b	7.5 ^b	7.5 ^b	7.5 ^b	7.5/5 ^{b,c}	5 ^b	5 ^b	NA ^b
16	Day 106 to Day 112	7.5 ^b	7.5 ^b	7.5 ^b	7.5 ^b	7.5 ^b	7.5 ^b	7.5/5 ^{b,c}	5 ^b	5 ^b	NA ^b
17	Day 113 to Day 119	7.5 ^b	7.5/5 ^{b,c}	7.5 ^b	7.5 ^b	7.5 ^b	7.5/5 ^{b,c}	7.5/5 ^{b,c}	5 ^b	5 ^b	NA ^b
18	Day 120 to Day 126	7.5/5 ^{b,c}	7.5/5 ^{b,c}	7.5/5 ^{b,c}	7.5/5 ^{b,c}	7.5/5 ^{b,c}	7.5/5 ^{b,c}	7.5/5 ^{b,c}	5 ^b	5 ^b	NA ^b
19	Day 127 to Day 133	7.5/5 ^{b,c}	7.5/5 ^{b,c}	7.5/5 ^{b,c}	7.5/5 ^{b,c}	7.5/5 ^{b,c}	7.5/5 ^{b,c}	5 ^b	5 ^b	5 ^b	NA ^b
20	Day 134 to Day 140	7.5/5 ^{b,c}	7.5/5 ^{b,c}	7.5/5 ^{b,c}	7.5/5 ^{b,c}	7.5/5 ^{b,c}	7.5/5 ^{b,c}	5 ^b	5 ^b	5 ^b	NA ^b
21	Day 141 to Day 147	7.5/5 ^{b,c}	5 ^b	7.5/5 ^{b,c}	7.5/5 ^{b,c}	7.5/5 ^{b,c}	5 ^b	5 ^b	5 ^b	5 ^b	NA ^b
22	Day 148 to Day 154	5 ^b	5 ^b	5 ^b	5 ^b	5 ^b	5 ^b	5 ^b	5 ^b	5 ^b	NA ^b

Table 6-4: Recommended corticosteroid tapering schedule

Week	Day	Corticosteroid dose ^a (mg/day; prednisone equivalent)											
23	Day 155 to Day 161	5 ^b	5 ^b	5 ^b	5 ^b	5 ^b	5 ^b	5 ^b	5 ^b	5 ^b	5 ^b	NA ^b	NA ^b
24	Day 162 to Day 168	5 ^b	5 ^b	5 ^b	5 ^b	5 ^b	5 ^b	5 ^b	5 ^b	5 ^b	5 ^b	NA ^b	NA ^b

NA=not applicable

^a Corticosteroid tapering is only required in those study participants receiving continuous corticosteroids at doses >7.5/day prednisone equivalent at the time of enrollment into the study.

^b Study participants starting at or achieving a dose of 7.5mg/day or lower may remain on this dose or taper at the discretion of the Investigator. This is indicated by cells with light grey font.

^c Alternating dosing every other day recommended to allow slow reduction based on standard tablet sizes

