Eligible study participants will have persisting active or relapsing-remitting SLE at screening visit (V1) despite stable SOC treatment (ie, antimalarials, corticosteroids, and/or immunosuppressants), in line with local and international guidance at screening visit (V1). Study participants considered to have a monophasic or an infrequent relapsing-remitting disease course (defined as no evidence for frequently flaring disease course and low risk to have frequent flares) will be excluded as their disease likely does not correspond to a persistent active or frequently relapsing SLE despite SOC treatment.

During the study, participants with a corticosteroid dose above a long-term tolerable level (7.5mg/day prednisone equivalent) will have to start corticosteroid tapering no later than the Week 8 Visit (Visit 4) to reach a target of 7.5mg/day or below. Investigators will be encouraged to start steroid tapering earlier if the condition of the study participant suggests improvement. Guidance will be provided on how to taper but the exact tapering regimen will be at the discretion of the Investigator to be adapted to the individual study participant's disease activity. Other SLE SOC treatment will have to be kept stable unless a reduction is indicated due to side effects. In case of insufficient improvement of disease activity, or a clinically relevant worsening of the disease activity, Investigators may initiate an escape treatment (Section 6.6.2) by increasing the dose of concomitant SOC medication. Depending on the nature of an escape treatment intervention, DZP may have to be discontinued if there is a safety concern. Investigators should discuss the impact of escape treatment use on study conduct with the Medical Monitor before initiation. In case of an initiation of escape treatment, study participants may be declared as **nonresponders** for the primary endpoint; however, they do not have to be withdrawn from the study.

Study participants will be encouraged to stay in the study under observation even if the study medication is discontinued (see Section 7.1). A study participant will have to be withdrawn from the study only if the study participant withdraws consent or a regulator, Institutional Review Board/Independent Ethics Committee (IRB/IEC), or the independent data monitoring committee (IDMC) requests a withdrawal for justified reasons (see Section 7.2).

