6.6.2 Escape medication

Although the use of escape medications is allowed at any time of the study, it should be delayed, if possible, for at least 8 weeks following the first administration of study treatment. Data from Phase 1 and Phase 2 studies suggest that DZP has a fast onset of action however it can take several weeks until the potential therapeutic effect of DZP fully develops. Escape treatment should be initiated as clinically indicated by the Investigator or other qualified physicians

treating the participant. Investigators should discuss the impact of escape treatment use on study conduct with the Medical Monitor before initiation.

Initiation of escape treatment may be handled as intercurrent event in estimands, which will be detailed in the statistical analysis plan (SAP) as described in Section 9.3.1. For the primary endpoint, specification of how escape treatment will be handled as an intercurrent event is detailed in Section 8.1.3.1, Section 9.3.1, and Section 9.6.

The date and time of escape medication administration as well as the name and dosage regimen of the escape medication must be recorded.

In case of use of escape treatment the study medication does not have to be automatically discontinued, however if the escape treatment in combination with DZP represents a safety concern (see Section 6.6) for the study participant the study medication should be discontinued but the study participant should remain in the study under observation. Investigators are advised to contact the Medical Monitor upfront if possible, to discuss the potential impact on the further study conduct in case study medications should be permanently discontinued.

The following escape medications may be used as indicated:

- Corticosteroids (new initiation or increase in dose)
- Immunosuppressants (new initiation or increase in dose):
 - azathioprine
 - methotrexate
 - mycophenolate mofetil
 - tacrolimus
 - low dose cyclophosphamide
 - cyclosporine
 - voclosporin

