8.1.3 Derived endpoints

8.1.3.1 BILAG 2004-based Composite Lupus Assessment

A study participant is considered to be a BILAG 2004-based Composite Lupus Assessment (BICLA) responder if all of the following is fulfilled:

1. BILAG 2004 improvement without worsening, defined as BILAG 2004 Grade As at Baseline Visit improved to B/C/D, and BILAG 2004 Grade Bs at Baseline Visit improved to C/D, and no BILAG 2004 worsening in other BILAG 2004 organ systems (that had BILAG 2004 Grade C, D, or E at Baseline) such that there are no new BILAG 2004 Grades A nor greater than 1 new BILAG 2004 Grade(s) B; and
2. No worsening in the SLEDAI-2K total score compared to Baseline Visit (defined as no increase in SLEDAI-2K total score); and
3. No worsening in the PGA compared to Baseline Visit (“no worsening” is defined as either no worsening or worsening $<10\%$ of the full 100mm VAS, equivalent to less than a 10mm increase in the PGA compared to Baseline Visit (V2) score).

Escape treatment intervention as indicated by Investigator until the assessment time point will be defined as intercurrent event for the primary endpoint leading to non-response from the day after the event onward.

Escape treatment intervention is defined as:

1. Any dose increase or new start of systemic antimalarials or immunosuppressants from Screening Visit and during Treatment Period
2. Any increase in dose or new start of a moderate to high potency topical immunosuppressant (eg, Tacrolimus) used for an organ system with SLE disease activity during the study
3. Any increase of prednisone equivalent dose within the first 4 weeks (up to Week 4) that is above the Baseline level by $>50\%$ of the Baseline level or of $>10\text{mg/day}$, whichever is higher, which does not return to the Baseline level within 7 days after increase above Baseline level
4. Any increase of prednisone equivalent dose for a SLE indication above Baseline level after Week 4
5. Any increase of prednisone equivalent dose by $>50\%$ or 5mg/day , whichever is lower, for more than 1 day within 8 weeks prior to an assessment for any indication after Week 4.
6. More than 1 corticosteroid intra-articular injection up to Week 12
7. Any corticosteroid intra-articular injection after Week 12 for an SLE indication
8. Any intramuscular administration of corticosteroid for an SLE indication
9. Any iv administration of corticosteroid for an SLE indication

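### The next-higher-column rule in Protocol 6.5.1.1 has no cap at the entry dose, so a literal reading starts a mandatory steroid taper with an increase for unlisted doses above 7.5 and below 30 mg/day

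*Protocol*

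**What the plan says.** Protocol Section 6.5.1.1 makes a taper mandatory for anyone on more than 7.5 mg/day prednisone equivalent. It must begin by Day 56 and aims at 7.5 mg/day or less by Week 18. After Screening the dose "should be kept stable onwards, if possible, or tapered".

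Table 6-4 sets out a schedule for starting doses of 40, 35, 30, 25, 20, 15 and 10 mg and for lower doses. For a screening dose that is not among them, "the tapering regimen of the next higher dose in the table should be used". Neither this sentence nor footnotes a to c of the table says that the scheduled dose may not exceed the participant's own. Unlisted doses can come from the protocol's own conversion step: "Steroid doses should be converted to prednisone equivalent doses prior to the assessment of study participant inclusion criteria", using Table 6-2.

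Two statements soften the rule. Table 6-4 is titled as a recommended schedule, and Section 4.1 says that "the exact tapering regimen will be at the discretion of the Investigator".

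For the primary endpoint, item 4 of the escape-treatment list in Section 8.1.3.1 reads "Any increase of prednisone equivalent dose for a SLE indication above Baseline level after Week 4". The lead-in to that list is "Escape treatment intervention as indicated by Investigator until the assessment time point will be defined as intercurrent event", and a blinded independent adjudicator confirms such events.

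**The concern.** Most columns of Table 6-4 open at their own starting dose. A participant moved to the next higher column therefore begins the taper on more steroid than at entry, although the section asks for a stable or falling dose. The direct consequence is avoidable steroid exposure in people who are meant to be reducing it. It also adds to the tertiary endpoint of total corticosteroid dose through Week 24.

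A possible second consequence follows from item 4, which has no size or duration threshold. If a table-assigned dose above Baseline after Week 4 were classed as escape treatment, the participant would be a BICLA non-responder without any worsening of disease.

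**Working it through.** **Inputs.** Table 6-4 by week; footnote c (split cells are taken on alternate days); Table 6-2 conversion factors; escape items 3, 4 and 5 in Section 8.1.3.1. The dose may not change during Screening, so entry dose d equals Baseline dose. Doses of 7.5 mg or less are left aside, because footnote a does not require them to be tapered. The column is assumed to run from Day 1.

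**The plan's own figure.** All days are at or below 7.5 mg from Week 14 in the 40, 30, 25 and 20 mg columns, from Week 13 in the 35 and 15 mg columns, and from Week 9 in the 10 mg column. The Week 18 aim is met.

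**Unlisted doses do arise.** Deflazacort 12 mg × 0.75 = 9 mg. Hydrocortisone 32 mg × 0.25 = 8 mg.

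**Mapping.** Column = smallest listed starting dose at or above d. The 10, 15 and 20 mg columns hold their starting dose for Weeks 1–4. The 25 and 30 mg columns hold it for Weeks 1–2 and then go to 20 mg. The 35 and 40 mg columns open at 30 mg. Change in Week 1 = (column dose − d)/d. Extra steroid = sum over days of max(column dose − d, 0).

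| Entry d (mg) | Week 1 dose (mg) | Change | Extra steroid, Weeks 1–8 |
|---|---|---|---|
| 8 | 10 | +25% | 28×2 + 14×2 = 84 mg |
| 9 | 10 | +11% | 28×1 + 14×1 = 42 mg |
| 11 | 15 | +36% | 28×4 = 112 mg |
| 12.5 | 15 | +20% | 28×2.5 = 70 mg |
| 17.5 | 20 | +14% | 28×2.5 = 70 mg |
| 22.5 | 25 | +11% | 14×2.5 = 35 mg |
| 27.5 | 30 | +9% | 14×2.5 = 35 mg |
| 32.5 | 30 | −8% | 0 |
| 37.5 | 30 | −20% | 0 |

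The band that is raised is exactly the unlisted doses above 7.5 and below 30 mg.

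**Weeks 5–8.** The 15 mg column is then at 10 mg and the higher columns are at 15 mg or less, so their entrants are below entry. The 10 mg column alternates 10 and 7.5 mg. Entrants above 7.5 and below 10 mg therefore exceed Baseline on 14 of 28 days and are below it on the other 14. The mean is (10 + 7.5)/2 = 8.75 mg, which exceeds Baseline only for entry doses under 8.75 mg.

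**Escape items.** Adjacent columns differ by at most 5 mg, so every rise is below 5 mg. Item 3 needs more than 10 mg or more than 50% of Baseline, whichever is higher, and is not met. Item 5 needs more than 50% or 5 mg, whichever is lower, and is not met: after Week 4 the largest rise is below 2.5 mg (under 34%). Only item 4 could apply. Read day by day, it covers entry doses above 7.5 and below 10 mg. Read on the average dose, it covers those above 7.5 and below 8.75 mg. Read on the average and only for an increase that begins after Week 4, it covers none, because the step up is in Week 1.

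**The case against.** The strongest reply is that no sensible Investigator would raise the dose. Section 6.5.1.1 provides for an increase only where it is medically indicated, its declared aim is reduction, and a taper that opens with a rise defeats its purpose. The natural reading is to follow the next column's downward steps from the participant's own dose, and a recommended table with Investigator discretion leaves room for that. Many conversions also land on listed doses: methylprednisolone 8, 12, 16, 24 and 32 mg, at a factor of 1.25, give 10, 15, 20, 30 and 40 mg. All of this stands as a limit on the practical effect. It does not correct the sentence, which names the column to use and contains no cap.

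A reader might infer that these participants become automatic non-responders under item 4. The documents do not support that. Section 4.1 ties escape treatment to disease: "In case of insufficient improvement of disease activity, or a clinically relevant worsening of the disease activity, Investigators may initiate an escape treatment". Section 6.6.2 adds: "Escape treatment should be initiated as clinically indicated by the Investigator". The adjudicator may therefore reject a dose that only follows the table. SAP Sections 4.2 and 4.5.1, which deal with prednisone-equivalent dose and with this escape definition, cannot be read in the public copy and may settle the matter, so nothing is counted as missing there.

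A reader might also infer a loss of power. The documents give no share of participants with such doses. As an assumed upper bound, suppose 2% of both arms were forced to non-response. Exact Fisher power with 104 and 208 participants would move from 0.911 (rates 0.32 and 0.52) to 0.901 (rates 0.32×0.98 and 0.52×0.98). That is an illustration, not a demonstrated effect.

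**Conclusion.** The point holds as a flaw in a stated dosing rule. How often it matters cannot be sized from the documents, and the number is probably small. The rule applies to both arms alike, so there is no reason to expect bias in either direction.

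It would be wrong to conclude that entrants between 7.5 and 10 mg stay above Baseline throughout Weeks 5–8, because the excess falls only on the alternate 10 mg days. The day counts and milligram totals depend on starting the column on Day 1. The protocol allows a start as late as Day 56 and does not say whether the table's days then run from the first infusion or from the start of the taper. The link to the primary endpoint remains a possibility that depends on the reading of item 4. Severity: optional.

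**What to change.** Add one sentence to Section 6.5.1.1: when the next higher column is used, the dose on each day is the lower of the entry dose and that column's dose, so that no taper dose exceeds the entry dose whenever the taper starts.

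An 8 mg entrant would take 8 mg in Weeks 1–4, then 8 and 7.5 mg on alternate days in Weeks 5–8 (or go straight to 7.5 mg if tablet sizes make that simpler), then 7.5 mg from Week 9. An 11 mg entrant would take 11 mg in Weeks 1–4 and 10 mg from Day 29. The day-by-day wording matters: holding 8 or 9 mg until both alternate-day values were at or below it would delay the first reduction to Day 57, one day past the limit. With the cap, no scheduled dose exceeds Baseline, every column still reaches 7.5 mg by Week 14 at the latest, and the item 4 question does not arise. Section 8.1.3.1 needs no change.

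The cost is one clarifying sentence. It helps only participants who have yet to start a taper, and the documents do not state the enrolment status. For those already past Week 8, a blinded listing of entry doses above 7.5 and below 10 mg/day would show whether any case needs the adjudicator's attention.
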